the 90-day FU to assess YMSM's satisfaction with the intervention, including the content, site layout and design, and general satisfaction. These domains are assessed on a 4-point response scale with individually specified anchors. The CSQ-8 has demonstrated high internal consistency across a large number of studies⁹⁵. The SEF and CSQ will take approximately 10 minutes to complete. We will also track users' actions in the intervention as process evaluation data. These data will include the number of times that they visited the site, their geographic location and the website from which they linked to our site, time spent in each session, number of times a user returns to a session, and which interactive features were "clicked on" during sessions.

Behavioral Assessments. The web surveys will be programmed to minimize out-of-range or inconsistent responses. Data exports will be automated into SPSS. The survey will be designed using best practices to encourage completion⁹⁶. Planned domains are listed below and may be refined based on the intervention content developed and YAB feedback. Based on our prior success in recruiting YMSM to complete online surveys, we will use best practices (e.g., surveys are dynamic and take less than 30 minutes to complete) to reduce participant burden. We have used all measures previously; scales have strong psychometric properties (i.e., adequate factor structure and $\alpha > .65$). Table 3 documents when domains will be assessed.

Table 3. Assessment Summary Table	BL	FU1	FU2	FU3
Sociodemographic Information				
Demographic data (e.g., race, sexuality)	X			
Social media use	X			
Changes in relationship, housing, work	X	X	X	X
Outcome indicators				
Sexual behavior	X	X	X	X
Recent HIV/STI test	X	X	X	X
Substance use	X	X	X	X
Predictors of Behavior Change				
TPB Constructs	X	X	X	X
Affective Motivations	X	X	X	X
Partner-seeking behaviors	X	X	X	X
Psychological Risk Correlates	X	X	X	X

information.

Outcome indicators: Consistent with our model, we have 3 primary risk reduction outcomes: increased consistent condom use across partner types (continuous), reduced number of UAI partners and occasions (continuous), and increased HIV/STI testing rates (dichotomous). We detail their assessment below:

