Sexual behaviors will be assessed using the Sexual Practices Assessment Schedule⁹⁷ used in previous online studies with YMSM to explore the number of occasions of different sexual acts (oral, anal; receptive, insertive) with different partner types. SPAS allows us to estimate the number of UAI partners and occasions across partner types, as well as the proportion of instances when condoms were not used^{70,98,99}. SPAS also ascertains YMSM's use of condoms during the past 30 days (1=Never/5=Always) and their HIV status disclosure practices with each partner. SPAS measures behaviors with male and female partners, respectively.

HIV/STI Testing Behaviors. We will ask YMSM to indicate the date of their more recent HIV and STI tests. Subsequently, we will ask participants to note if they have ever been medically diagnosed as having one or more STIs, the date of their most recent STI test if available, and whether a medical provider had previously diagnosed them with a STI. At each FU, we will ask participants whether they have gone to get tested for HIV and/or STIs, respectively. If tested, participants were asked to indicate what tests they received and whether they had been medically diagnosed as having HIV or STI. At FU, we will ask YMSM whether they have had any changes in their HIV status. Newly diagnosed cases will be asked if they were linked to care.

Psychosocial indicators of behavior change. To measure *TPB constructs*, we will measure YMSM's attitudes, subjective norms, self-efficacy using previously tested scales with MSM^{7,100,101}. We will use existing items measuring condom use intentions with different partner types, and self-efficacy to negotiate condoms with different partner types¹⁰². Descriptive and personal norms will be measured separately for different partner types (1=Strongly Disagree/Strongly Agree)¹⁰⁰. We will measure these constructs at baseline and FUs.

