Estimation of parameters for a subsequent R01. Consistent with the R34 mechanism, the primary role of this pilot RCT is to ensure that the critical parameters required to plan a large trial are estimated as informatively as possible. Certain principles then follow: (1) If alterations are necessary to address measurement or performance problems, these will be permitted in an effort to establish optimal procedures and design parameters before a future trial, precisely so that no changes in protocol will be required during a future trial; and, (2) Estimation of critical design parameters with point and confidence interval estimates will be considered highly important, as large sample sizes are not required to locate these parameters adequately when planning for a subsequent trial. As a result, we are not powered to estimate small effect sizes or carry out sophisticated statistical analyses; rather, we seek to estimate key study parameters with sample means and proportions together with two-sided 95% confidence intervals, and test the primary null hypotheses at the

traditional two-sided level $\alpha=.05$.

To test for intervention effects over time with pilot RCT data, we will use the general framework of generalized

linear mixed models (GLMM) to model the longitudinal outcome trajectories¹¹⁰⁻¹¹². Note that some of our outcomes

are binary, some count and some continuous traits and thus need to be treated differently. The general form of the GLMM will be $(\mu_{ij}) = \beta_{0i} + \beta_{cov} Covariates_{ij} + \beta_{visit} Visit_j +$

Table 4. Detectable Effect (.80 power, alpha=.05)	N = 140	N = 160	N = 180
Continuous Outcomes			
Within-subject correlation (rho=.4)	.39	.35	.33
Within-subject correlation (rho=.5)	.41	.38	.35
Within-subject correlation (rho=.6)	.44	.40	.37
Binary Outcomes (p(NTHP)=.40)			
Within-subject correlation (rho=.4)	2.19	2.04	1.93
Within-subject correlation (rho=.5)	2.31	2.14	2.02
Within-subject correlation (rho=.6)	2.43	2.24	2.11

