$\beta_{Trt} Trt_i + \beta_{Trt \times visit} rt_i \times Visit_j$, where μ_{ij} is the mean response corresponding to subject *i* on visit *j* (*baseline and three follow-ups*), *g* denotes the link function (identity for continuous outcome, logit for binary outcome and natural log for count outcomes); $Trt_i = 1$ if the *i*-th subject is in the MEET-ME group and 0 if the *i*-th subject is in the NTHP group. The variable Visit can be coded in different ways depending upon how one wants to model the effect of time on the mean response. For example, for characterizing only pre vs. post effect Visit can be coded as a binary indicator with 0 representing baseline and 1 representing post-randomization; Assuming a linear time trend, Visit can be coded as 0, 1, 2, 3, or it can be simply coded as a categorical variable representing the distinct effect of each visit compared to the baseline. The interaction coefficients $\beta_{Trt \times Visit}$ are of interest here, measuring the difference in the rate of change in outcome across the two treatment groups at each visit. If the baseline outcome measure is included as a part of the covariates on the right hand side of the

NCT02842060

above equation, then we only have three repeated measures on the left hand side of the model ($j=1,2,3$) and we can look at average treatment effect across visits without including the $Trt \times Visit$ interaction term. In this particular case, the GLMM analysis with continuous outcome will be equivalent to a repeated measures analysis of covariance after adjusting for baseline values. The subject-specific random intercepts β_{0i} are assumed to be normally distributed with a common variance and they account for within-person correlation. We will also explore if we need a subject specific random-slope corresponding to visit in the above model. Maximum likelihood estimation will be used for fixed effect parameters. Models will be compared according to information criterion like AIC, BIC. For some binary outcomes like STI/HTV testing, we will perform an aggregate analysis after collapsing across the repeated measures using simple logistic regression comparing whether the probability of having tested at least once over the entire FU period is different across treatment groups, after adjusting for baseline values. To ensure robustness, we will also apply an exchangeable working correlation structure to its corresponding generalized estimating equation (GEE) model.

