Power for primary analysis: As shown in Table 4, we will have 80% power to detect a medium intervention effect (Cohen's $d > .35$) at $\alpha=.05$ in a continuous measure using a repeated measures group design (N=180) with 4 observations (baseline + 3 FUs) when the standard deviation is 1 and the correlation between observations on the same subject (ρ) is 0.6. For dichotomous outcomes, we estimate 80% power at $\alpha=.05$ to detect an odds ratio of 2.11 or greater assuming that the proportion for the intervention condition is .58 and the attention-control condition is .40, with ρ also being .60. We note that there is some controversy regarding the use of "pilot data" to estimate the actual effect size, as specified by Kraemer et al.¹¹³. We agree with their view that clinically meaningful effect sizes should be decided based on extrinsic, clinical judgment grounds, and not based on the pilot data which are too few, typically, to obtain reliable conclusions. However, we can use these data to rule out unusually large or small effects through standard 95% confidence interval procedures. Thus, we will confirm that extrinsic effect sizes are contained within our confidence intervals¹¹³ and use these Even with 20% attrition, we will have preliminary effects with adequate error margins to inform the subsequent trial.

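### The primary UAI partner and occasion outcomes are counts but are labelled continuous, so their link and estimand conflict, and the count model names no distribution or visit-level dispersion

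*Combined protocol and SAP*

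**What the plan says.** All references are to the combined protocol and SAP.

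- **Behavioral Assessments, Outcome indicators.** Three primary risk-reduction outcomes are listed, each with a data type. Condom use is continuous and HIV/STI testing is dichotomous. The third is "reduced number of UAI partners and occasions (continuous".
- **Sexual behaviors.** The instrument is the Sexual Practices Assessment Schedule: "SPAS allows us to estimate the number of UAI partners and occasions across partner types".
- **Estimation of parameters for a subsequent R01.** The outcomes "are binary, some count and some continuous traits and thus need to be treated differently". The generalized linear mixed model uses "identity for continuous outcome, logit for binary outcome and natural log for count outcomes". The subject-specific intercepts "are assumed to be normally distributed with a common variance and they account for within-person correlation". Fixed effects are estimated by maximum likelihood, a random slope on visit may be explored, and models are compared by AIC or BIC. For robustness, "we will also apply an exchangeable working correlation structure to its corresponding generalized estimating equation (GEE) model". The plan will also "test the primary null hypotheses at the" two-sided 5% level.
- **Power for primary analysis and Table 4.** The text says "we will have 80% power to detect a medium intervention effect" for a continuous measure with SD 1, and gives an odds ratio for a binary one. There is no row for counts.

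**The concern.** Taken at its word, the outcome list sends UAI partners and occasions to the identity link. The count provision then serves none of the primary outcomes. Taken by data type, UAI goes to the log link. The first reading estimates a difference in means and the second a ratio of rates. The plan intends to check whether externally chosen effect sizes lie inside its 95% intervals, and that check needs one scale.

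Under the count reading, the random intercept absorbs stable differences between men. It does not absorb extra variation from one visit to the next within the same man. If that variation exists and the likelihood has no place for it, the standard error of the treatment-by-visit coefficient, which the plan singles out as the quantity of interest, is too small. Both the 5% test and the 95% interval suffer. Dispersion is also a parameter the next trial will need, and the plan does not commit to estimating it.

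**Working it through.** **1. The plan's own figures.** Inputs: 120:60, four observations, SD 1, 80% power, two-sided 5%, so the multiplier is 1.960 + 0.842 = 2.802. The detectable effect is d = 2.802 × √{[(1 + 3ρ)/4] × (1/60 + 1/120)}.

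- ρ = .4: 2.802 × √(.550 × .025) = .329 (Table 4: .33)
- ρ = .5: 2.802 × √(.625 × .025) = .350 (Table 4: .35)
- ρ = .6: 2.802 × √(.700 × .025) = .371 (Table 4: .37)

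The binary row at N = 180 also reproduces: 1.936, 2.022 and 2.108 against 1.93, 2.02 and 2.11. At N = 180 the table is sound for the two data types it covers.

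**2. Size of the test if the count likelihood is Poisson.** The documents give no UAI mean or dispersion and never name Poisson, so everything in this step is assumed. Let v be the variance of a visit-level multiplier with mean 1 (v = 1/shape). Simulated rejection of a true null for treatment × post, Poisson random-intercept model, nominal 5%:

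| Mean | v | Subject effect | Replicates | Rejection |
|---|---|---|---|---|
| 2 | 0 | normal, SD .8 | 400 | 7% |
| 1 | .5 | normal, SD .8 | 400 | 12% |
| 2 | .5 | normal, SD .8 | 400 | 27% |
| 2 | 1 | normal, SD .8 | 400 | 36% |
| 3 | 1/3 | gamma, shape .8 | 120 | 27% |
| 3 | 1/1.5 | gamma, shape .8 | 120 | 49% |

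The mean-3 rows use 96:48, which is 120:60 after 20% attrition. A negative binomial model on the same two settings rejected 7% (v = 1/3) and 3% (v = 1/1.5).

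A rough formula agrees in direction. With variance inflation φ = 1 + v × mean, the size is 2 × [1 − Φ(1.96/√φ)].

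- Mean 1, v = .5: φ = 1.5, size 11%
- Mean 2, v = .5: φ = 2, size 17%
- Mean 2, v = 1: φ = 3, size 26%

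It runs below most of the simulated values because it ignores the spread of subject means.

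The 49% is the least certain figure. Its Monte Carlo error is 1.96 × √(.49 × .51/120), about 9 points. In that setting the mean model standard error was .122 against an empirical SD of .281. Then 1.96 × .122/.281 = .85, a two-sided tail of about 39%. A 100-replicate run with likelihood-ratio tests gave 38% for the same setting and 22% for v = 1/3. A conditional-Poisson version gave 14 to 37% across overdispersed settings.

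**3. The identity-link reading.** At 96:48, mean 3 and a true rate ratio of .6, the identity-link treatment-by-visit model held its size. Its power was 43% against 50% for a log-link GEE with robust variance in one dispersion setting, and 61% against 72% in another.

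**4. A detectable rate ratio on the log scale.** With negative binomial shape s, control mean μ₀ and μ₁ = RR × μ₀:

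Var(log RR) = [(1 + 3ρ)/4] × [(1/μ₀ + 1/s)/60 + (1/μ₁ + 1/s)/120], solved for |log RR| = 2.802 × √Var.

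At μ₀ = 3, ρ = .6, s = 1, try RR = .646, so μ₁ = 1.94. Var = .7 × [1.333/60 + 1.516/120] = .0244, and exp(−2.802 × .1562) = .646. For s = .5 and .3 the answers are about .56 and .49.

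**The case against.** Four points on the other side deserve weight.

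**The plan does not say Poisson.** A reader might infer that its primary test is invalid. The documents do not support that. They leave the distribution unnamed, and the inflation in the working is conditional on a default that the analyst might not use.

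**There are safeguards.** The same section allows a random slope, compares models by AIC or BIC and adds a GEE check. In the 100-replicate run (Monte Carlo error about 2 to 5 points), adding a random slope cut rejection to 14% (v = 1/1.5) and 7% (v = 1/3). A log-link exchangeable GEE with sandwich variance gave 5% and 7%. This stands in part. The slope is optional and did not fully cure the heavier setting. Robust variance is not stated for the GEE, and its sentence follows directly on the binary testing analysis, so whether it covers counts is unclear. No candidate distributions are named for the AIC/BIC step.

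**The conflict may be loose wording.** The outcome list may simply contrast numeric with dichotomous measures, with the analysis section refining this later. That is plausible, but the analysis section never says which outcomes are counts.

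**It is a pilot.** It disclaims power for small effects and aims mainly to estimate parameters. A missing count row in Table 4 is therefore only missing detail. A reader might also translate d = .37 at mean 3 into RR = 1 − .37 × √(3 + 9/s)/3, which is .57, .43 and .29 for s = 1, .5 and .3, and conclude that a 43 to 71% reduction is needed. That holds the control-arm SD in both arms, although a negative binomial SD falls with the mean. The log-scale calculation gives .65, .56 and .49. The pilot argument does not remove the main point, because primary nulls are still tested at 5% and interval estimates are the stated product.

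**Conclusion.** The concern holds as an internal conflict over the data type, link and estimand of a primary outcome, together with an underspecified count model. That the log link is meant for UAI is an inference, though no other primary outcome is a number of events.

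The practical size depends on assumptions that the documents cannot settle: a Poisson likelihood, means of 1 to 3 and moderate visit-level dispersion. Under them the treatment-by-visit test rejects about 12 to 49% of the time, with the top of that range probably somewhat high. Without visit-level overdispersion it is near nominal, about 3 to 7%. The identity-link branch is valid in size but less powerful, by 7 and 11 points in the two settings tried. Both readings do worse than a properly specified count analysis, so this is a cheap improvement worth making. It does not show that the planned test is invalid or that Table 4 is wrong for the outcomes it covers.

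**What to change.** 1. In the outcome list, label both number of UAI partners and number of UAI occasions as counts.
2. In the analysis section, name the UAI analysis: a negative binomial mixed model with log link, or a log-link GEE with robust (sandwich) variance. If the GEE stays as a check, say that it covers the count outcomes and state its variance estimator.
3. Report rate ratios with 95% confidence intervals. If the negative binomial model is used, also report the estimated dispersion for planning the next trial.
4. Optionally, add a rate-ratio row to Table 4, computed on the log scale over stated means and dispersions. At 120:60, ρ = .6 and mean 3, the entries would be about .65, .56 and .49 for shape 1, .5 and .3, all three inputs being assumptions.

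The cost is SAP wording and a little analysis work. Intervals may be wider than under Poisson. Design, data collection and sample size do not change.

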compared to those who reported only a single type of partner. These findings suggest that single YMSM may have difficulties enacting safer sex strategies if they have different types of sexual relationships over the same period of time. Thus, we propose to develop an intervention that equips YMSM who engage in UAI with opportunities to reinforce safer sex negotiation skills with different sexual partner types.

In a manuscript currently under review in *AIDS & Behavior* (see Appendix A), we also noted that YMSM who reported greater desire for a future relationship (relationship ideation) were less likely to report multiple types of URAI partners and most likely to note that all their partners were romantic interests. Conversely, YMSM who reported higher limerence scores and who believed that foregoing condoms would help create intimacy with a sexual partner were more likely to report having multiple types of partners in the prior two months. These findings underscore the importance of acknowledging the different cognitive and affective processes that may be associated with YMSM's sexual decision-making. Although we have begun to acknowledge the distinction between partner types when discussing sexual risk-taking behaviors⁵⁻¹⁰, we have yet to develop an intervention that helps YMSM distinguish between these partner types and select appropriate partner-specific HIV/AIDS risk reduction strategies. Consequently, our intervention activities will aid YMSM

reflect on their partner-seeking behaviors, develop sexual decision-making rules to reduce their HIV/AIDS risk, and consider various relationship typologies when making sexual health decisions.

INNOVATION

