Phase 3: Pilot Testing the Intervention through a small RCT. The purpose of Phase 3 is to evaluate the MEET-ME intervention as a pilot study using a prospective randomized control trial design⁸⁶. This design (see Table 2) benefits our study in three ways: (1) the longitudinal structure provides a method for analyzing change

NCT02842060

in outcome objectives over time, (2) it also allows for analysis of individual differences in response to treatment, and (3) randomization maximizes the internal validity of the study by creating equivalent groups at pretest⁸⁶. Our primary outcomes will be YMSM's consistent condom use, number of UAI partners and occasions, and HIV/STI testing behaviors. To avoid overwhelming participants with assessments and/or confounding results with practice effects, we will only collect outcome data via online surveys at 30, 60, and 90 day FUs. FUs are important as YMSM may require time to contemplate and apply the intervention's content into their partner-seeking and sexual behaviors. As a pilot, we recognize that we may not have sufficient power to detect small effect sizes; however, this design will inform our subsequent large-scale RCT, allowing us to identify and address implementation and retention challenges that could arise in the larger trial. Specifically, the primary purposes of this pilot trial are: 1) to demonstrate the feasibility of the methods proposed for a subsequent trial; 2) to stabilize procedures that are replicable; and 3) to determine important parameters with sufficient accuracy to reliably estimate sample size and power for a future RCT.

Table 2. RCT Design

Baseline	Randomization	Condition	FU 1 (30 d)	FU 2 (60 d)	FU 3 (90 d)
○	R	MEET-ME (N = 120)	○	○	○
○		NHTP (N= 60)	○	○	○

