Recruitment. Our intended sample size across both conditions is N=180 (MEET-ME, n=120; NHTP, n=60). We include a 2:1 ratio so we may increase our ability to examine the MEET-ME condition in greater detail. Candidates must (1) be male at birth and identify as male, (2) be between the ages of 18 and 24 (inclusive), (3) self-report as single, (4) self-report as HIV-negative, (5) speak and read English, and (6) report UAI with a male partner in prior 6 months. Consistent with the Internet's potential reach, we will allow YMSM from around the country to participate in the intervention. We will reach the population using social media ads on Facebook and Twitter. Promotional materials will describe the study and provide a 1-800 number to call to verify eligibility. Once determined eligible, YMSM will receive a code to access the site.

Once YMSM enter our website, we will verify that participants live in the US using the American Registry for Internet Numbers (ARIN) regional IP codes and zip codes. Participants will complete a 30 minute baseline questionnaire and be randomized in a 2:1 ratio into the MEET-ME or NHTP site. As part of the baseline questionnaire, we will ask participants to provide information that may help us contact them for FU assessments and verify that they are not fraudulent or duplicate entries^{87,88}. We will use best practices^{89,90} to retain participants (e.g., comprehensive locator information that includes participants' cell phone number, e-mail, Facebook and/or Skype username, and contact information for 2 peers who could help us contact them).

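### Does the primary outcome of consistent condom use need a stated measure and a stated score for a window without anal sex?

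*Combined protocol and SAP*

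**What the plan says.** Outcome indicators lists "increased consistent condom use across partner types (continuous") among the primary outcomes, and the Phase 3 design section repeats the set as "consistent condom use, number of UAI partners and occasions, and HIV/STI testing behaviors".

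The Sexual behaviors section names the instrument, the Sexual Practices Assessment Schedule (SPAS), and two quantities that could serve. One is a rating of "use of condoms during the past 30 days (1=Never/5=Always"), where higher is better. The other is described by "as well as the proportion of instances when condoms were not used", where higher is worse. Neither is designated as the outcome.

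Phase 3 Recruitment requires men to "report UAI with a male partner in prior 6 months", so a 30-day window without anal sex is possible at any visit.

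Data Analyses gives the generalized linear mixed model (GLMM), with an identity link for continuous outcomes. Several forms are allowed: "for characterizing only pre vs. post effect Visit can be coded as a binary indicator", and another that begins "If the baseline outcome measure is included as a part of the covariates". The section on parameters for a subsequent R01 tests the primary null hypotheses at two-sided .05.

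**The concern.** A man who has no anal sex in the window has no condom score. The proportion is 0/0, and no not-applicable category is described for the rating. Three treatments seem open: leave the window unscored, score it 1 because no condom was used, or score it 5 because no act was unprotected. The same man counts as a success on the primary UAI-occasion outcome, where he is zero.

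If MEET-ME changes how many men are sexually active, the codings can give different answers on a primary outcome, and someone could choose among them after seeing the data. The rule for combining partner types is also missing. The Significance section reports men with several partner types, "compared to those who reported only a single type of partner", so men will differ in how many types contribute to the score.

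**Working it through.** **Inputs.** From the documents: 120 and 60 men, four visits, SD 1, within-man correlation ρ = 0.6, two-sided .05, 80% power. Assumed, because the documents give no figures: the share q of windows without anal sex, the arm gap in that share, a mean rating of 3 among active NTHP men, and a benefit δ of 0 or 0.4 rating points.

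**1. The plan's own figure.** Table 4 follows from

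d = (1.96 + 0.84) × √[((1 + 3ρ)/4) × (1/120 + 1/60)] = 2.80 × √(0.70 × 0.025) = 2.80 × 0.1323 = 0.37,

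as stated for N = 180 and ρ = 0.6. It assumes a score for every man at every visit, so it does not settle the coding.

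**2. What a fixed score would do.** Let empty windows score c. With shares q_T (MEET-ME) and q_C (NTHP) at follow-up, and no arm difference at baseline, the expected arm difference is

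(1 − q_T) × δ + (q_T − q_C) × (c − 3).

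| q_T, q_C | δ | c = 1 | c = 5 | unscored |
|---|---|---|---|---|
| .30, .30 | 0.4 | 0.70 × 0.4 = +0.28 | +0.28 | +0.40 |
| .40, .30 | 0 | 0.10 × (−2) = −0.20 | +0.20 | 0 |
| .45, .30 | 0 | 0.15 × (−2) = −0.30 | +0.30 | 0 |
| .45, .30 | 0.4 | 0.22 − 0.30 = −0.08 | 0.22 + 0.30 = +0.52 | +0.40 |

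Scores 5 and 1 differ by 4 × (q_T − q_C) whatever condom use is. With equal shares both codings only shrink the effect. A reversal in expectation needs an arm gap. The unscored column assumes that stopping anal sex is unrelated to a man's condom score. If those who stop come from one risk tail, scenario runs put the bias at no more than about 0.10 SD either way.

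**3. What leaving windows unscored costs.** For the treatment-by-post term with complete data, the standard error is

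√[(1 − ρ) × (1 + 1/3) × 0.025] = √(0.5333 × 0.025) = 0.1155,

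so detectable d = 2.80 × 0.1155 = 0.32. If each window is empty independently with probability q, the factor 0.5333 is replaced by the value from the generalized least squares information averaged over the 16 visit patterns:

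| q | factor | standard error | detectable d |
|---|---|---|---|
| .20 | 0.712 | 0.133 | 0.37 |
| .30 | 0.850 | 0.146 | 0.41 |
| .40 | 1.045 | 0.162 | 0.45 |

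For a true effect of 0.38 SD, power falls from about 91% to about 74% at q = .30 (0.38/0.1458 − 1.96 = 0.65). Table 4's method would show a milder rise, from 0.37 to 0.38, 0.39 and 0.40, because it averages all four visits and does not test the interaction.

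**4. Which treatment the plan points to.** No section assigns 1 or 5 to an empty window. Phase 2 Procedures has the team check the survey's skip patterns, and Behavioral Assessments describes dynamic surveys programmed to limit inconsistent answers. A man with no partner in the window would most naturally skip the item. The missing-data text relies on a mixed model, which uses whatever visits are scored. This is an inference, but each piece points to leaving the window unscored.

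**The case for a change.** The strongest case for a change is that this is a primary outcome tested at .05, and that the pilot exists to estimate parameters for the next trial: the effect, SD and within-man correlation all depend on the coding. The two candidate quantities invite opposite defaults, since zero unprotected acts looks best and never using a condom looks worst. In simulations with no effect at all, each coding is significant about 5% of the time, but at least one of the three is significant in 11% to 12% of trials. Writing the rule down would cost only a few words.

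Much of this stands. The outcome variable is not designated, and the questionnaire that might settle it is not in the documents. The 11% to 12%, however, supposes an analyst who tries all three codings and reports the best. Scoring an abstinent man as never using a condom is the least natural reading, yet it produces the reversal.

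Leaving windows unscored is not free of difficulty either. It compares men selected on behavior after randomization, which sits uneasily with intention to treat. In the baseline-covariate form it also drops men unscored at baseline: at 30%, 180 × 0.70 = 126 remain. Whether to prefer that comparison, or one model form over the other, is a matter of judgment and does not correct an error. The primary UAI-occasion count remains defined, at zero, for these men.

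**Conclusion.** The concern identifies missing detail, not a stated rule that gives a wrong result. The harmful codings are not in the plan, and the natural handling of a 0/0 or a skipped item is to leave it unscored. Under that handling the expected estimate stays at the true effect when only activity changes, provided stopping anal sex is unrelated to condom use.

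The possible shifts of 0.20 to 0.30 points with no condom effect rest on assumed arm gaps of 10 to 15 points in empty windows. The documents give neither the gap nor the share. With equal shares, even the poor codings only shrink the effect, to 70% of its size when 30% of windows are empty.

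The precision cost of the sensible default is real: detectable d rises from about 0.32 to 0.37, 0.41 or 0.45 at 20%, 30% or 40% empty windows varying by visit, with ρ = 0.6 and no dropout. But that cost comes from men having no condom use to report, and wording would not remove it. The plan already lets assessment domains be refined and measurement problems be addressed, so analysts can name the variable and the partner-type rule within it. No change is required.
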